8.2 Primary Efficacy Analysis

We will test the hypothesis that pregnant women who receive IPTp with either 3 dose DP or monthly DP will have a lower risk of placental malaria defined by histopathology compared to those who receive 3 doses of SP. We will also compare the two different dosing strategies of DP.

Primary Outcome: The primary outcome will be the prevalence of placental malaria based on placental histopathology and dichotomized into any evidence of placental infection (parasites or pigment) vs. no evidence of placental infection. We will also evaluate placental malaria defined by histopathology as a categorical variable (active-acute, active-chronic, and past infection) based on the criteria developed by Rogerson et al.²⁶

Analysis Method: A modified intention-to-treat approach to all will be used, including all study participants randomized to therapy with the primary outcome measured, regardless of whether the intervention was not given for any reason.

Primary analysis. We will compare the prevalence of placental malaria defined by histopathology at birth between the study arms using the Chi-Square or Fisher's exact test for all pair-wise comparisons and presented as the risk ratio (RR) or reduction of the RR ($1 - RR \times 100\%$) if the RR is lower than 1. We will explore for any differences of potential confounders between the treatment arms and if necessary adjust our analysis using multivariate logistic regression.

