Estimated number of pregnant women enrolled	100	100		100	
Estimated number with placental outcomes	90	90		90	
Assigned treatment arms in infants	q 3 monthly DP	q 3 monthly DP	monthly DP	q 3 monthly DP	monthly DP
Estimated number of infants enrolled	90	45	45	45	45
Estimated number of infants reaching 24 months of age	81	41	41	41	41

Table 5. Minimum relative differences in outcomes detectable given estimated effective sample sizes

Hypothesis	Analysis population	Control group and estimated sample size	Comparison group and estimated sample size	Estimated outcome measure in control group	Minimum relative difference detectable*
1	Pregnant women with placental malaria measured by histopathology at birth	3 dose SP (n=90)	3 dose DP or monthly DP (n=90 each)	Prevalence of placental malaria = 62%	33%
		3 dose DP (n=90)	monthly DP (n=90)	Prevalence of placental malaria = 20-50%	41-70%
2	Infants 0-24 months of age born to women assigned to receive IPTp with 3 dose DP or monthly DP	Infants assigned q 3 monthly DP (n=90)	Infants assigned monthly DP (n=90)	Incidence of malaria = 3-5 episode PPY	18-23%
3	Infants 0-24 months of age randomized to q 3 monthly DP	Infants of women assigned 3 dose SP (n=90)	Infants of women assigned 3 dose DP or monthly DP (n=45 each)	Incidence of malaria = 3-5 episodes PPY	22-28%
	Infants 24-36 months of age after chemoprevention stopped	Infants assigned q 3 monthly DP (n=163)	Infants assigned monthly DP (n=82)	Incidence of malaria = 3-5 episodes PPY	16-21%

* Relative difference = (estimated outcome in control arm – estimated outcome in the comparison arm) / estimated outcome on the control arm (two-sided alpha = 0.05, power = 80%).

6 General Considerations

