6.3 Covariates and Subgroups

(ICH E3; 9.7.1, 11.4.2.1. ICH E9; 5.7)

Covariates of interest will include baseline measures of maternal age, gestational age at enrollment, gravidity, bednet ownership, socio–economic status as estimated by a household wealth index, and prevalence of malaria parasites using LAMP.

Sub–group analyses will be performed based on categories of maternal age, gravidity, and gestational age at the time study drugs were first administered.

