7.2 Baseline Characteristics

Skeleton table of all baseline variables collected on the day of enrollment that will be presented are provided in Table 8 below.

Table 8. Baseline characteristics of study participants randomized to IPTp

Characteristic	Treatment arm		
	3 dose SP (n=XXX)	3 dose DP (n=XXX)	Monthly DP (n=XXX)
Age in years, mean (SD)			
Gestational age in weeks, mean (SD)			
Gestational age categories, n (%)			
12–16 weeks			
>16–20 weeks			
Previous pregnancies, n (%)			
0			
1			
≥ 2			
Bednet ownership, n (%)			
None			
Untreated net			
ITN			
Household wealth index, n (%)			
Lowest tertile			
Middle tertile			
Highest tertile			
Weight in kg, mean (SD)			
Height in cm, mean (SD)			
Laboratory values, mean (SD)			
WBC count per mm ³			
Neutrophil count per mm ³			
Platelet count per mm ³			
Hemoglobin g/dL			
ALT IU/L			
Detection of malaria parasites by LAMP, n (%)			

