8.3 Secondary Efficacy Analyses

Secondary Outcomes: Secondary outcomes will include maternal outcomes during pregnancy and birth outcomes as listed in Table 10.

Analysis Method: A modified intention-to-treat approach will be used, including all study participants randomized to therapy with data on the secondary outcomes, regardless of whether the intervention was not given for any reason.

Secondary analyses. We will compare proportions between the study arms using the Chi-Square or Fisher's exact test for all pair-wise comparisons and presented as the risk ratio (RR) or reduction of the RR ($1 - RR \times 100\%$) if the RR is lower than 1. For repeated measures in the same study participant (maternal parasitemia and anemia during pregnancy) we will use generalized estimating equations with a log-binomial family and robust standard errors. We will compare the incidence of symptomatic

malaria during pregnancy using Poisson or negative binomial regression models. The Poisson models will include the logarithm of the follow-up time as an offset. We will translate the fitted coefficients and their confidence bounds into percentage effects with the formula $100 * [\exp(\text{coefficient}) - 1]$. This approach is closely related to exponential survival models for analyzing events per follow-up time, but is better able to adjust for violated assumptions. Testing for overdispersion in the Poisson regression can detect violations of these assumptions, and variances can be adjusted accordingly to produce valid p-values and confidence intervals. If significant deviations from required distributions in study data are detected, we will employ negative-binomial or zero-inflated negative-binomial models to account for the observed pattern of data. If necessary, multivariate analyses will be performed to adjust for potential confounders and effect modifiers. Comparisons of incidence measures will be expressed at the incidence rate ratio (IRR) or the protective efficacy ($PE = 1 - IRR \times 100\%$).

Skeleton tables for the presentation of primary and secondary efficacy outcomes are presented in Tables 11 and 12 below.

Table 11. Outcomes assessed at the time of delivery

Outcome	Treatment arm						
	3 dose SP ^a		3 dose DP		Monthly DP		
	Prevalence	Prevalence	RR (95% CI)	p-value	Prevalence	RR (95% CI)	p-value
Malaria positivity, by test							
Histopathology	n/N (%)	n/N (%)			n/N (%)		
Placental blood by microscopy	n/N (%)	n/N (%)			n/N (%)		

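### SAP 8.2 adjusts the primary comparison only if baseline differences appear, and by logistic regression although an RR is reported; adjustment should use fixed covariates on the RR scale

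*SAP*

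**What the plan says.** Under the primary analysis, SAP section 8.2 compares the arms by a chi-square or Fisher's "exact test for all pair-wise comparisons and presented as the risk ratio (RR"). It continues: "We will explore for any differences of potential confounders between the treatment arms and if necessary adjust our analysis using multivariate logistic regression". It gives no test or threshold for when adjustment becomes necessary.

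Section 6.3 does list covariates: "Covariates of interest will include baseline measures of maternal age, gestational age at enrollment, gravidity, bednet ownership", then socio-economic "status as estimated by a household wealth index, and prevalence of malaria parasites using LAMP". That makes six. All six are tabulated at baseline in Table 8 (section 7.2), for example "Detection of malaria parasites by LAMP, n" (%). Section 8.2 does not refer to this list.

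For reporting, section 8.3 says: "Skeleton tables for the presentation of primary and secondary efficacy outcomes are presented in Tables 11 and 12 below". Table 11 has one RR with 95% CI and one p-value for each DP arm against SP, and no adjusted column. For secondary outcomes section 8.3 has a parallel sentence: "If necessary, multivariate analyses will be performed to adjust for potential confounders and effect modifiers".

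**The concern.** Three things are fixed badly.

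- **Trigger.** Adjustment waits for differences between randomised arms. Such differences carry no information about whether a covariate matters. A strongly prognostic covariate is worth adjusting for even when the arms are balanced, and a non-prognostic one is not worth it even when they differ.
- **Covariates.** The potential confounders of section 8.2 are not said to be the six of section 6.3, so the model's content is left until the data have been seen.
- **Scale and standing.** Logistic regression yields an OR, while section 8.2 and Table 11 report an RR, and no conversion is named. Nor does the SAP say whether an adjusted result would replace the unadjusted one or support it.

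At stake are some power, and a clear answer if the adjusted and unadjusted results fall on opposite sides of 5%.

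**Working it through.** **1. The plan's own figure.** Inputs from section 5 and Table 5: control-arm "Prevalence of placental malaria = 62"%, 90 evaluable women per arm, two-sided alpha 0.05, power 80%. The unadjusted two-proportion formula is

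n per arm = [1.96·√(2p̄(1−p̄)) + 0.84·√(p₁(1−p₁) + p₂(1−p₂))]² / (p₁ − p₂)².

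Solved at n = 90, the smallest detectable relative reduction is 33.4% from 62%, 40.6% from 50% and 69.8% from 20%. Table 5 states 33% and 41–70%, so it rests on the unadjusted test. At exactly 33%, p₂ = 0.62 × 0.67 = 0.4154. Power with 90 per arm is then 78.9% by this formula and 77.6% by exact binomial calculation for the chi-square test.

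**2. The scale gap at the Table 5 effects.** OR = [p₂/(1−p₂)] / [p₁/(1−p₁)].

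| p₁ | p₂ | RR | OR |
|---|---|---|---|
| 62% | 41.5% | 0.67 | 0.44 |
| 50% | 29.5% | 0.59 | 0.42 |
| 20% | 6% | 0.30 | 0.26 |

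An unconverted logistic estimate cannot go into Table 11's RR column.

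**3. How often chance alone would trigger adjustment.** The SAP names no test, so this is an assumption. For one pair of arms and independent covariates, six screened at p<0.05 give 1 − 0.95⁶ = 26.5%. At p<0.10, two give 1 − 0.90² = 19% and six give 1 − 0.90⁶ = 47%. The simulation below gave 18% and 45%.

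**4. Power, by simulation.** There were 90 women per arm, 62% versus 41.54%, and 20,000 trials per setting. Assumed, not in the SAP: two binary covariates (30% primigravid, 50% LAMP-positive), outcome ORs as shown, and a trigger at p<0.10. Fixed adjustment is modified Poisson on the two covariates. Triggered adjustment replaces the chi-square by logistic regression. In the six-covariate row, the four extra covariates are unprognostic.

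| Covariate ORs | 1/1 | 2/2 | 3/3 | 3/6 |
|---|---|---|---|---|
| Chi-square only | 77.7% | 77.2% | 78.0% | 77.5% |
| Always adjusted | 78.1% | 80.0% | 82.5% | 85.5% |
| Triggered, two screened | 77.7% | 77.9% | 79.1% | 79.5% |
| Triggered, six screened | 77.7% | 78.6% | 80.1% | 81.5% |

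In the three prognostic settings, the gain over chi-square is 2.8, 4.5 and 8.0 points for fixed adjustment. It is 0.7, 1.1 and 2.0 for the trigger on two covariates, and 1.4, 2.1 and 4.0 for the trigger on six. The trigger thus captures about a quarter of the available gain with two screened, and about half with six. With unprognostic covariates the methods differ by at most 0.4 points.

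**5. Conflicting verdicts.** In the prognostic settings, the trigger fires and the two tests disagree at 5% in 1.9–3.3% of all trials (two screened) or 3.8–6.2% (six).

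**6. Type I error.** With 62% in both arms, the exact size of the chi-square is 5.26%. Replacing it by the logistic test after a trigger gives 4.5–5.2% (two screened) or 4.8–5.2% (six), across all four covariate settings and 40,000 trials each.

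**7. Cost if the covariates are unprognostic.** With N = 180 and k covariate degrees of freedom, the expected R² of treatment on the covariates is k/(N−1). Gravidity in three levels, LAMP result and gestational age use k = 4, so 4/179 = 2.2%. The SE then widens on average by 1/√(1 − 0.022) − 1 ≈ 1.1%; the 95th percentile in simulation is 2.8%.

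**The case against.** **The SAP is less open than the sentence suggests.** Section 6.3 lists covariates, so it would be wrong to say the SAP has none; only the link from section 8.2 is missing. The unadjusted RR is also the natural default: it is named first, Table 11 has room for one RR per comparison with SP, and Table 5 reproduces from the unadjusted test. A reader might infer that the primary result is undefined. The document does not support going that far, although a default reading is still not a stated rule.

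**An unadjusted primary test is legitimate.** This stands. It matches the sample size, and preferring an adjusted test is a matter of efficiency. Declaring the unadjusted RR primary would therefore settle the ranking but recover none of the power in step 4.

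**The power figures rest on assumptions.** This also stands. The covariate prevalences, the ORs and the trigger are not in the SAP.

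**Type I error.** A reader might infer that data-dependent adjustment inflates it. The trigger looks at covariates and not at outcomes, the logistic test is valid, and step 6 shows error near 5%. Higher figures need the smaller p-value to be chosen: 5.4–5.7% if this is done after a trigger with two covariates screened, 5.7–6.3% with six, and 5.6–7.3% if done in every trial. The SAP plans no such choice.

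**Conclusion.** The point holds as one of method and clarity. Section 8.2 ties adjustment to chance imbalance, does not connect the model to the covariates of section 6.3, and names a model whose estimate is not on the reported scale. The scale gap follows from the SAP's own prevalences (RR 0.67 against OR 0.44). The loss of power is conditional: with two prognostic covariates of OR 2 to 6 and a p<0.10 trigger on those two, fixed adjustment adds about 3 to 8 points and triggered adjustment about 1 to 2. With unprognostic covariates there is little or no difference. Neither bias nor an inflated type I error is shown. The change should be made because it improves the analysis at almost no cost.

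**What to change.** In section 8.2, replace the sentence on exploring differences with one adjusted analysis, run whatever the baseline table shows. Fix its covariates in advance from section 6.3, for example gravidity (0, 1, ≥2), baseline LAMP result and gestational age at enrolment. Report an RR with 95% CI for each pairwise comparison, from modified Poisson regression with robust variance, a log-binomial model, or logistic regression standardised to a marginal RR.

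State in advance which RR is primary. Only an adjusted primary RR captures the power gain. Keeping the unadjusted RR primary matches Table 5 and needs the least change; the adjusted RR is then labelled supportive.

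In section 8.3, replace the conditional wording with the same fixed covariates on each outcome's own scale (RR for proportions, IRR for incidence). Keep the effect-modifier analyses.

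The cost is SAP wording and a few lines of code. The example covariates are already in Table 8, so no new data are needed and the sample size does not change. There are two downsides. If the example covariates prove unprognostic, the SE is about 1% wider on average, and somewhat more in some trials. A rule is also needed for any woman without a baseline LAMP result.

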8.3 Secondary Efficacy Analyses

Secondary Outcomes: Secondary outcomes will include maternal outcomes during pregnancy and birth outcomes as listed in Table 10.

Analysis Method: A modified intention-to-treat approach will be used, including all study participants randomized to therapy with data on the secondary outcomes, regardless of whether the intervention was not given for any reason.

Secondary analyses. We will compare proportions between the study arms using the Chi-Square or Fisher's exact test for all pair-wise comparisons and presented as the risk ratio (RR) or reduction of the RR ($1 - RR \times 100\%$) if the RR is lower than 1. For repeated measures in the same study participant (maternal parasitemia and anemia during pregnancy) we will use generalized estimating equations with a log-binomial family and robust standard errors. We will compare the incidence of symptomatic

malaria during pregnancy using Poisson or negative binomial regression models. The Poisson models will include the logarithm of the follow-up time as an offset. We will translate the fitted coefficients and their confidence bounds into percentage effects with the formula $100 * [\exp(\text{coefficient}) - 1]$. This approach is closely related to exponential survival models for analyzing events per follow-up time, but is better able to adjust for violated assumptions. Testing for overdispersion in the Poisson regression can detect violations of these assumptions, and variances can be adjusted accordingly to produce valid p-values and confidence intervals. If significant deviations from required distributions in study data are detected, we will employ negative-binomial or zero-inflated negative-binomial models to account for the observed pattern of data. If necessary, multivariate analyses will be performed to adjust for potential confounders and effect modifiers. Comparisons of incidence measures will be expressed at the incidence rate ratio (IRR) or the protective efficacy ($PE = 1 - IRR \times 100\%$).

Skeleton tables for the presentation of primary and secondary efficacy outcomes are presented in Tables 11 and 12 below.

Table 11. Outcomes assessed at the time of delivery

Outcome	Treatment arm						
	3 dose SP ^a		3 dose DP		Monthly DP		
	Prevalence	Prevalence	RR (95% CI)	p-value	Prevalence	RR (95% CI)	p-value
Malaria positivity, by test							
Histopathology	n/N (%)	n/N (%)			n/N (%)		
Placental blood by microscopy	n/N (%)	n/N (%)			n/N (%)		
Placental blood by LAMP	n/N (%)	n/N (%)			n/N (%)		
Maternal blood by microscopy	n/N (%)	n/N (%)			n/N (%)		
Maternal blood by LAMP	n/N (%)	n/N (%)			n/N (%)		
Cord blood by microscopy	n/N (%)	n/N (%)			n/N (%)		
Cord blood by LAMP	n/N (%)	n/N (%)			n/N (%)		
Birth outcomes							
Spontaneous abortion	n/N (%)	n/N (%)			n/N (%)		
Stillbirth ^b	n/N (%)	n/N (%)			n/N (%)		
Low birth weight ^b	n/N (%)	n/N (%)			n/N (%)		
Preterm delivery ^b	n/N (%)	n/N (%)			n/N (%)		
Congenital anomaly ^b	n/N (%)	n/N (%)			n/N (%)		
Composite adverse birth outcome	n/N (%)	n/N (%)			n/N (%)		

^a Reference group

^b Only includes those at least 28 weeks gestational age

Table 12. Longitudinal outcomes assessed during pregnancy

Outcome	Treatment arm						
	3 dose SP ^a		3 dose DP		Monthly DP		
Incidence measures	Events ^b	Events ^b	IRR (95% CI)	p-value	Events ^b	IRR (95% CI)	p-value
Symptomatic malaria	xx (x.xx)	xx (x.xx)			xx (x.xx)		
Prevalence measures	Prevalence	Prevalence	RR (95% CI)	p-value	Prevalence	RR (95% CI)	p-value
Detection of malaria parasites by LAMP							
All routine visits	n/N (%)	n/N (%)			n/N (%)		
20 weeks gestational age	n/N (%)	n/N (%)			n/N (%)		
24 weeks gestational age	n/N (%)	n/N (%)			n/N (%)		
28 weeks gestational age	n/N (%)	n/N (%)			n/N (%)		
32 weeks gestational age	n/N (%)	n/N (%)			n/N (%)		
36 weeks gestational age	n/N (%)	n/N (%)			n/N (%)		
40 weeks gestational age	n/N (%)	n/N (%)			n/N (%)		
Anemia defined as hemoglobin level < 11 g/dL							
All routine visits and delivery	n/N (%)	n/N (%)			n/N (%)		
20 weeks gestational age	n/N (%)	n/N (%)			n/N (%)		
28 weeks gestational age	n/N (%)	n/N (%)			n/N (%)		
36 weeks gestational age	n/N (%)	n/N (%)			n/N (%)		
At the time of delivery	n/N (%)	n/N (%)			n/N (%)		

^a Reference group

^b Number of events (incidence per person year at risk)

9 Safety and Tolerability Analyses

Safety and tolerability will be evaluated during the period following the 1st dose of study drug administration through the end of the observation period (6 weeks post-partum) or premature study withdrawal.

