4.5 Study Variables

(ICH E3; 9.5.1. ICH E9; 2.2.2)

See Data Dictionary Excel file for complete list of study variables.

Table 2. Schedule of routine assessments and procedures in pregnant women

Evaluations and Interventions	Enrollment	Weeks of gestation							Delivery	1 and 6 weeks postpartum
		16*	20	24	28	32	36	40		
Informed consent	X									
HIV testing ¹	X				X				X	
Pregnancy confirmation ²	X									
Obstetrical ultrasound ³	X									
Blood collected by phlebotomy for CBC, ALT, and immunology studies	X		X		X			X	X	
Blood collected by finger prick for dried blood spot and plasma	X	X	X	X	X	X	X	X	X	
Routine assessment in the study clinic ⁴	X	X	X	X	X	X	X	X		X
Administration of study drugs		X	X	X	X	X	X	X		
Collection of cord blood and placental tissue									X	
Labor and delivery documentation ⁵									X	

* Only if study subject enrolled prior to 16 weeks gestation; If the woman is enrolled between 18-20 weeks, then the week 20 phlebotomy will not be performed.

Explanation of maternal schedule of events

1. HIV test will be done at enrollment and documented. A repeat rapid HIV test will be done at delivery. HIV testing shall be done using standard rapid HIV-testing algorithm.
2. Pregnancy confirmation by positive urine pregnancy test, or confirmed intrauterine pregnancy by ultrasound. A pregnancy test may be skipped if an intrauterine pregnancy has been noted on ultrasound at the screening visit.
3. Ultrasound will be done to confirm intrauterine pregnancy and estimate gestational age at enrollment. See Appendix B for dating criteria.
4. Targeted physical exam will include anthropometric measurements (e.g. weight) and vital signs (i.e. temperature, pulse, and blood pressure). Measurement of height at the enrollment visit only.
5. Labor & Delivery documentation will include: Peripartum history, mode of delivery, Apgar scores (when available), weight, length, and head circumference of the child at birth, approximate gestational age, duration of labor, signs of fetal distress (presence of meconium), summary of events in first days of life (including feeding, breathing patterns, jaundice, lethargy, or any additional abnormal findings), duration of admission if delivered in hospital.

Table 3. Study Case Report Forms

CRF#	Form/Questionnaire
1	BC-1 Screening
2	BC-1 Enrollment
3	BC-1 Clinic Visit Form
4	BC-1 Subject Hospital Admission
5	BC-1 Missed Visit Form
6	BC-1 Subject Death Record Form
7	BC-1 Mothers Delivery Form
8	BC-1 Postpartum Visit Form

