Low birth weight	Secondary outcome	Proportion	At delivery	Birth weight < 2500 gm	Deliveries \geq 28 weeks gestational age	Withdrawn prior to delivery or < 28 weeks gestational age or no birth weight	Inferred if no birth weight but weight available with 7 days of birth
Preterm delivery	Secondary outcome	Proportion	At delivery	Gestational age < 37 weeks	Deliveries \geq 28 weeks gestational age	Withdrawn prior to delivery or < 28 weeks gestational age	None
Congenital malformation	Secondary outcome	Proportion	At delivery	Any congenital malformation documented on exam	Deliveries \geq 28 weeks gestational age	Withdrawn prior to delivery or < 28 weeks gestational age or infant unavailable for examination	None
Composite adverse birth outcome	Secondary outcome	Proportion	At delivery	Any of the following: spontaneous abortion, stillbirth, low birth weight, preterm delivery, or congenital malformation	All deliveries	Withdrawn prior to delivery	None
Symptomatic malaria during pregnancy	Secondary outcome	Incidence	Time at risk during pregnancy	Number of episodes of fever and positive blood smear by microscopy	Duration of observation from day following 1 st dose of study drugs to delivery or premature study withdrawal	None	None
Parasitemia during pregnancy detected by LAMP	Secondary outcome	Proportion	At the time of each routine visit	Maternal blood samples with parasites detected by LAMP	Routine visits at 20, 24, 28, 32, 36, and 40 weeks of gestational age following 1 st dose of study drugs to delivery or premature study withdrawal	Missed routine visits or samples not collected	None
Maternal anemia	Secondary outcome	Proportion	At the time of each routine visit and at delivery when phlebotomy done	Hemoglobin level < 11 g/dL	Routine visits at 20,28, 36 weeks of gestational age following 1 st dose of study drugs to delivery or premature study withdrawal	Missed routine visits or sample not collected when scheduled for phlebotomy	None

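### The maternal anaemia model does not pre-specify enrolment haemoglobin, the outcome's own baseline; the unadjusted comparison is valid but less precise than data already scheduled would allow

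*SAP*

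**What the plan says.** Table 10 (SAP 8.1) defines maternal anaemia as "Hemoglobin level < 11 g/dL", measured as follows: "At the time of each routine visit and at delivery when phlebotomy done". The visits are 20, 28 and 36 weeks plus delivery, and only those after the first dose count. The enrolment value is therefore a pre-treatment measurement and not part of the outcome.

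SAP 8.3 sets the method: "For repeated measures in the same study participant (maternal parasitemia and anemia during pregnancy) we will use generalized estimating equations". The model in full is "generalized estimating equations with a log-binomial family and robust standard errors". It names no covariate. Adjustment is conditional: "If necessary, multivariate analyses will be performed to adjust for potential confounders and effect modifiers". Neither the trigger nor the covariate set is fixed.

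SAP 6.3 begins its list: "Covariates of interest will include baseline measures of maternal age, gestational age at enrollment, gravidity, bednet ownership". It goes on to a household wealth index and baseline parasite prevalence by LAMP. Haemoglobin is not named.

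Enrolment haemoglobin will nevertheless be available. Table 2 (4.5) marks enrolment for the row "Blood collected by phlebotomy for CBC, ALT, and immunology studies", and Table 8 (7.2) reports "Hemoglobin g/dL" by arm among the baseline laboratory values.

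**The concern.** The baseline value of the measurement that defines an outcome is usually a strong predictor of it. A woman with low haemoglobin at enrolment is more likely to be below 11 g/dL later, whatever her arm. Leaving this between-woman variation in the error term widens the interval for the risk ratio. It also leaves any chance imbalance in starting haemoglobin inside the estimate.

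The list in 6.3 is uneven here. It names baseline LAMP, the counterpart of parasitaemia, which is the other repeated outcome in the same sentence of 8.3. It does not name the counterpart of anaemia. Because adjustment depends on an undefined judgement of need, any later use of haemoglobin would be a choice made after the data are seen.

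A practical problem follows. If the team adds haemoglobin as a continuous covariate to the family named in 8.3, the fit may not converge or may give risks of 1 or more.

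**Working it through.** **The plan's own figures.** The SAP states no power, prevalence, standard deviation, correlation or precision for anaemia, so there is no anaemia figure to reproduce. The nearest is Table 5: a 33% relative difference from 62% with 90 women per arm. With p1 = 0.62 and p2 = 0.62 × 0.67 = 0.4154, the unpooled formula gives n = (1.960 + 0.842)² × (0.62×0.38 + 0.4154×0.5846) / (0.2046)² = 89.7, hence 90. This supports 90 evaluable women per arm and nothing more.

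**Assumed inputs.** These are within-woman correlation r between enrolment and later haemoglobin, anaemia prevalence p, and number of later values k. Table 10 allows up to four values. Women enrolled at 18-20 weeks have no week-20 phlebotomy (Table 2 note), so some have fewer.

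**Analytic guide.** With latent normal haemoglobin and equal correlations, the proportional variance reduction for a woman's mean of k anaemia indicators is

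R² = [r·φ(c)]² / [p(1−p)] × k / [1 + (k−1)·ρ_bin],

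where c is the normal cut-point for p and ρ_bin is the correlation between two binary indicators. At p = 0.5 and r = 0.5, φ(0) = 0.399 and ρ_bin = (2/π)·arcsin(0.5) = 0.333.
- k = 1: (0.5×0.399)²/0.25 = 0.159, a 16% reduction.
- k = 3: 0.159 × 3/1.667 = 0.286, a 29% reduction.

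At k = 1 the formula gives 4-6% at r = 0.3 and 12-16% at r = 0.5, for prevalence 20-50%. This is the case for the visit-specific rows of Table 12.

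**Simulated trials.** The table shows squared standard error of the log risk ratio, adjusted divided by unadjusted.

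| r | 95 per arm, k = 3, p 30-45% | 90 per arm, k = 3, p 30-45% | 90 per arm, k = 4, p 20-50% |
|---|---|---|---|
| 0.3 | 0.91 | about 0.90 | 0.87-0.90 |
| 0.4 | 0.85 | not run | 0.81 |
| 0.5 | 0.75-0.76 | 0.75-0.77 | 0.72-0.75 |
| 0.6 | 0.68-0.70 | 0.68-0.71 | 0.66 |

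The first column gives the 9-32% range. On the log scale the interval narrows by 1 − √0.91 = 5% to 1 − √0.68 = 18%. In women, 90/0.91 = 99 to 90/0.68 = 132 per arm would give the same precision unadjusted. With an assumed haemoglobin SD of 1.3 g/dL and a 0.4 g/dL shift, power rises from 49-65% to 57-72%.

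**Chance imbalance.** With the same SD, the standard error of the between-arm enrolment difference is 1.3 × √(2/90) = 0.19 g/dL, a 95% range of ±0.38. At r = 0.5 about ±0.19 g/dL carries into later values.

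**Can the named family take the covariate?** Failure means no convergence or a fitted risk of 1 or more.
- Log-binomial with continuous haemoglobin, k = 4, r = 0.3: 1-10% failures at prevalence 20-30%, and 25-29% at prevalence 50%.
- Same model at higher r: 35% (r = 0.4, prevalence 30%), 53-95% (r = 0.5), 95% (r = 0.6, prevalence 30%).
- Same model, k = 3, prevalence 30-45%: 30-47% (r = 0.3), 83-98% (r = 0.5), 97-100% (r = 0.6). With 95 per arm, r = 0.5 and prevalence 45%, 110 of 120 fits failed.
- Log-binomial with baseline anaemia yes/no: no failures, with squared standard error cut by 7-12% (r = 0.3) and 20-27% (r = 0.5).
- Log-link Poisson GEE with robust standard errors and continuous haemoglobin: an estimate in every run.

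The runs disagree on the failure rate at r = 0.3, so no exact rate should be relied on there. They agree that failure is frequent from r = 0.5.

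**The case against.** The strongest reply is that nothing here is an error. Under randomisation the unadjusted GEE is unbiased in expectation and its type I error is controlled. Anaemia is one of many secondary outcomes, and no sample size rests on it. All of that stands, and it limits the point to precision and pre-specification.

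Three stronger readings are tempting, and the SAP does not support them.
- A reader might infer that the log-binomial model cannot take baseline haemoglobin. It can take baseline anaemia as yes/no without difficulty, and continuous haemoglobin in some settings. Nor does the SAP plan a log-binomial model with continuous haemoglobin, and the model it does name, without that covariate, is not shown to fail.
- A reader might infer that even the optional adjusted analysis would leave haemoglobin out. The list in 6.3 is not worded as closed, and 8.3 does not restrict adjustment to it. An imbalance visible in Table 8 could be adjusted for. The accurate statement is that haemoglobin is not pre-specified.
- A reader might take 9-32% as a property of this trial. Every input behind it is assumed. Across wider assumptions the analytic range runs from about 4% (one visit, r = 0.3) to 50% (four visits, r = 0.7).

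It is also fair that a variance reduction sounds larger than its effect on the interval, and that the simulated power gain is only 7-8 points. The gain remains real wherever haemoglobin tracks within women, and it costs no data.

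**Conclusion.** The point holds as a worthwhile improvement, not as a flaw that invalidates the analysis. SAP 8.3 leaves the anaemia comparison without a pre-specified covariate, 6.3 does not name haemoglobin, and the rule for adjustment is undefined, although the outcome's own baseline is scheduled for every woman.

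Under the assumptions set out above, the avoidable variance in the all-visits comparison is about 9-32%, and it is smaller for single visits. If the correlation is below 0.3, the gain falls further: 5% in simulation at r = 0.2 with four visits. The choice of family matters only once continuous haemoglobin enters the model; then log-binomial fitting is unreliable when anaemia is common or the correlation is moderate to high.

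**What to change.** In 8.3, give maternal anaemia its own sentence: a GEE with log link, Poisson working variance and robust standard errors, with arm, visit and continuous enrolment haemoglobin always in the model. This keeps the risk ratio that Table 12 reports. A workable alternative keeps the log-binomial family and enters baseline anaemia as yes/no, at a somewhat smaller gain.

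Add haemoglobin to the covariates in 6.3, and report the unadjusted risk ratio beside the adjusted one.

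The cost is one sentence in 8.3, one word in 6.3 and an extra column or footnote in Table 12. No visit, sample or data item is added. The change should be made before unblinded anaemia data are seen, so that the covariate is not chosen from the results.
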